9.5.2 Peri reperfusion blood pressure

Mean blood pressure in the 5 minutes before and in the 5 minutes after reperfusion.

Was adrenaline given?

Were other inotropes given or increased in dosage?

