5.6 Study endpoints

5.6.1 *Primary endpoint*

- Post reperfusion intra-operative blood loss
- Feasibility of adding TPA and FFP to livers undergoing normothermic perfusion before transplantation

5.6.2 *Secondary endpoint*

- Return to theatre in first 24 hours for bleeding
- Total and post reperfusion intra-operative blood transfusion
- Liver utilisation: proportion of liver perfusions resulting in a transplant
- Incidence of symptomatic anastomotic and non-anastomotic strictures at 6 months post-transplant
- Incidence of any anastomotic or non-anastomotic stricture excluding those related to hepatic artery thrombosis
- Incidence of “clinically relevant” non-anastomotic strictures, using the van Rijn definition¹¹
- Incidence of post reperfusion syndrome: 30% fall in mean BP lasting at least a minute in the first 5 minutes post reperfusion or the need for adrenaline or doubling of noradrenaline to support the circulation.
- Early allograft function (Olthoff criteria¹² and MEAF score¹³)
- Incidence of hepatic artery thrombosis in the first 6 months
- Incidence of acute kidney injury (RIFLE criteria)
- D-dimer release into perfusate compared to controls

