10.4.2 Post reperfusion syndrome

Defined as a fall in mean arterial pressure of 30% for one minute in the first 5 minutes post reperfusion of the liver compared to the 5 minutes before reperfusion, or the requirement for adrenaline in that period.

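### The pressure and drug items listed in section 9.5.2 do not capture what the post-reperfusion syndrome endpoint needs

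*Protocol*

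**What the plan says.** The protocol defines post-reperfusion syndrome twice and lists the data for it once.

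- **Section 5.6.2 (secondary endpoints).** The pressure limb is "30% fall in mean BP lasting at least a minute in the first 5 minutes post reperfusion". The alternative drug limb is "the need for adrenaline or doubling of noradrenaline to support the circulation".
- **Section 10.4.2 (response criteria).** The pressure limb is a "fall in mean arterial pressure of 30% for one minute in the first 5 minutes post reperfusion of the liver", with the 5 minutes before reperfusion as the reference. The drug limb is "or the requirement for adrenaline in that period". Noradrenaline is not mentioned.
- **Section 9.5.2 (what is recorded).** There are three items: "Mean blood pressure in the 5 minutes before and in the 5 minutes after reperfusion"; whether adrenaline was given; and "Were other inotropes given or increased in dosage".

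Nothing else in section 9 asks for a peri-reperfusion pressure or a vasopressor dose. Section 11.3 gives an expected incidence of 30%. It places the syndrome among the expected events that will not be reported as adverse events to the ethics committee or sponsors.

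**The concern.** An endpoint can be derived only from what is recorded. Both definitions need to know how low the pressure went and for how long within a 5-minute window. Section 9.5.2 asks for neither. The definition in 5.6.2 also needs to know whether noradrenaline was at least doubled, and 9.5.2 asks neither for that drug by name nor for any dose.

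A qualifying fall could therefore go unseen, and a trivial change in a vasopressor could be taken for a qualifying one. With three centres, each could resolve the ambiguity in its own way. Where the pressure limb cannot be applied, classification leans on whether adrenaline was given, which is a treatment decision in an open-label study. Because section 11.3 takes the syndrome out of adverse event reporting, this endpoint is the main planned place where an excess would show.

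**Working it through.** **Inputs.** Fall of 30% for one minute within 5 minutes (5.6.2 and 10.4.2); two 5-minute windows (9.5.2); expected incidence 30% (11.3); 60 recipients (10.2). The protocol states no power or precision figure for this endpoint, so there is none to reproduce.

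**Step 1: pressure, if 9.5.2 is read as one average per window.** Let the fall be a fraction *f* lasting *d* minutes. Assume that pressure is at the pre-reperfusion level for the rest of the window; the documents do not state this.

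- Fall shown by the 5-minute average = *f* × *d*/5.
- Depth needed for that average to show 30% = 0.30 × 5/*d*.

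| Duration of fall (min) | A 30% fall reads as | Depth needed for the average to read 30% |
|---|---|---|
| 1 | 0.30 × 1/5 = 6% | 150% (impossible) |
| 2 | 0.30 × 2/5 = 12% | 75% |
| 3 | 0.30 × 3/5 = 18% | 50% |
| 4 | 0.30 × 4/5 = 24% | 37.5% |
| 5 | 0.30 × 5/5 = 30% | 30% |

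Under this reading and this profile, no one-minute fall can reach the threshold, although any one-minute fall of 30% or more meets both definitions. A fall lasting the whole window is preserved.

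**Step 2: pressure, if 9.5.2 is read as mean arterial pressure observed through each window.** Nothing is averaged away. The list still names no lowest value, duration or sampling interval, so what is written down is left to the person completing the record.

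**Step 3: drugs.**

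| Limb | 5.6.2 | 10.4.2 | Obtainable from 9.5.2? |
|---|---|---|---|
| Adrenaline | yes | yes, within the 5-minute period | yes, as yes/no, though the item carries no time window of its own |
| Noradrenaline doubled | yes | absent | no |

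A 10% increase in noradrenaline, a doubling of it and the start of a different inotrope all give the same yes. This needs no assumption about the pressure profile.

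**Step 4: how many events.** 0.30 × 60 = 18 expected. The protocol does not say how many of these would qualify by pressure alone, how deep or long the falls are, or which definition the 30% refers to. The number affected could lie anywhere from none (every fall is sustained, or the patient also receives adrenaline) to all 18 (every event is a brief fall without adrenaline, recorded as an average).

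**The case against.** The best reply is that mean blood pressure ordinarily means mean arterial pressure, not a 5-minute average. Section 5.6.2 uses the similar phrase mean BP for something that can last a minute, and 10.4.2 writes mean arterial pressure for the same criterion. On that reading, 9.5.2 tells sites to note arterial pressure in two windows, and the arithmetic in Step 1 does not bite. This reading is at least as plausible as the other, and nothing in the protocol says that events are scored from an average. What remains is that neither reading asks for the lowest value or its duration.

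Two stronger conclusions are tempting, and the documents do not support them.

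- A reader might infer that most events would be lost. That would need the depth, duration and recovery of the falls, none of which is given. It also ignores adrenaline, a recorded alternative that would identify some patients whose fall is missed.
- A reader might infer that the recorded data fail both definitions entirely. That is too strong for drugs: 10.4.2 has only an adrenaline limb, and adrenaline is recorded. The noradrenaline gap concerns 5.6.2 alone.

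It is also fair to say that this is one secondary endpoint of a pilot. With one transplanted liver in six as control, about 60/6 = 10 recipients receive FFP-only livers, so the randomised comparison will be imprecise however the endpoint is recorded. That limits the consequence but does not remove the mismatch. Nor can the matter simply be left to a statistical analysis plan, which cannot supply values that were not collected. Anaesthetic records may hold them, but the protocol does not say that they will be used.

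**Conclusion.** The point holds: following 9.5.2 as written does not yield the endpoint.

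- **Noradrenaline.** The gap is certain for 5.6.2, because a doubling cannot be told from a smaller increase. Sections 5.6.2 and 10.4.2 also disagree on whether this limb belongs to the endpoint.
- **Pressure.** The lowest value and duration are not requested on any reading. The loss of a one-minute 30% fall (read as 6%) depends on taking one average per window and on pressure being at baseline for the rest of it.
- **Size.** The share of the roughly 18 expected events affected cannot be determined from the document, and no percentage should be attached to it.

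This is a data-capture gap in a secondary safety endpoint. It does not touch the primary endpoint, but it is cheap to close.

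**What to change.** Reconcile 5.6.2 and 10.4.2 to a single endpoint definition, stating whether the noradrenaline limb is part of it. Then have 9.5.2 list:

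- mean arterial pressure averaged over the 5 minutes before reperfusion;
- lowest mean arterial pressure sustained for at least one minute in the 5 minutes after reperfusion;
- adrenaline given in that period (yes/no);
- if the noradrenaline limb is kept, the rate immediately before reperfusion and the highest rate in the 5 minutes after.

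Derive the endpoint from these values. A one-minute 30% fall would then read as 30%, and a doubling would be a rate ratio of 2 or more. Extract the same items for the comparators, including the previously perfused recipients in 10.6, where records allow.

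The cost is a change of wording and slightly more transcription from the anaesthetic record for each case, with no new procedure.

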9.5.3 Recordings in the first week

- ALT days 1 to 10
- INR days 1 to 10
- Bilirubin days 1 to 10
- Platelets days 1 to 10
- Peak creatinine in first 7 days

9.5.4 Assessment at 6 months

- Graft survival
- Patient survival
- Result of MRCP if one has been done

10 Statistics

10.1 Study statistician

Statistical analysis will be undertaken by a member of the research team, either [name] or designated deputy.

10.2 Number of Subjects to be enrolled

60 subjects in total, 30 DBD and 30 DCD. This will represent around 45 DCD and 35 DBD livers needing to be perfused. It is anticipated this will be 35-45 per site.

10.3 Sample size considerations

This is a pilot study of the safety and efficacy of *ex situ* thrombolytic therapy to assess whether a full clinical trial of the treatment is warranted. The TPA perfused livers and the number of transplants will be compared to the control perfusions .

10.4.2 Post reperfusion syndrome

Defined as a fall in mean arterial pressure of 30% for one minute in the first 5 minutes post reperfusion of the liver compared to the 5 minutes before reperfusion, or the requirement for adrenaline in that period.

10.4.3 Early allograft dysfunction

Early allograft dysfunction will be measured by two methods. In the Olthoff method, it is defined by either a rise in transaminases (ALT or AST) to over 2000u/L between 1 and 7 days post-transplant, or an INR>1.6, or a bilirubin >10mg/dL (171 µmol/L) on day 7¹². Treatment and comparator groups will also be compared by the model for early allograft function (MEAF) score, a continuous score out of 10 reflecting variables measured in the first 3 days¹³.

10.4.4 Acute kidney injury

Acute kidney injury will be defined by the RIFLE criteria as a creatinine in the first 7 days post-transplant which has risen more than two-fold higher than the pre-transplant value, or the need for haemofiltration or dialysis. The peak to baseline values will also be compared.

The ratio of peak (d1-7) over baseline creatinine will also be recorded and compared with historical comparators; the absolute percentage where the ratio is ≥ 2.0 will also be compared.

10.4.5 Survival (patient and graft)

These will be measured from the date of transplant and will be reported for all deaths and graft failures both due to rejection and due to all causes.

10.5 Statistical methods to be employed

Descriptive data will be presented as median, interquartile range or range (continuous variables) or number, percentage (categorical variables) and compared using the Kruskal-Wallis test (continuous variables) and Fisher's exact test (categorical variables). Survival will be compared with log rank analysis.

10.6 Analysis plan

Transplant recipients in the pilot study will be compared with twice the number of recipients of DCD livers that were machine perfused in the recipient centres in the previous 2 years. They will be matched for agonal phase duration, cold ischaemia time and UK donor liver index ¹⁶.

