4.1 Introduction

There are two sorts of deceased organ donors, those certified dead by brain stem criteria (DBD donors) and those certified dead by circulatory criteria (DCD donors). Brain dead donors are confirmed dead and brought to the operating theatre for organ removal while still on a ventilator. The heart is still beating and there is still a blood supply to the organs up to the point they are cooled *in situ* and removed. Circulatory death donors, on the other hand, usually have some sort of brain catastrophe but do not fulfil criteria for brain stem death, but nevertheless future treatment is considered futile and not in their interests. The patients have their treatment withdrawn, ventilation stopped, and after a period of minutes to hours the circulation stops. Death is verified after 5 minutes of circulatory arrest, after which the donor is brought around to the operating theatre, the organs are flushed *in situ* and then removed. Hence there is a period of many minutes where the organs are warm but without a blood supply, a state termed warm ischaemia.

In the UK in 2019/20 there were 1580 deceased organ donors, two thirds of which were DBD and a third DCD¹. Livers were used from 76% of DBD donors and only 27% of DCD donors, largely because of uncertainty regarding the effects of the period of warm ischaemia. DCD donor livers have a higher incidence of never working (primary non function, 4%), more initial poor function (around 30%)², and a high incidence of bile duct strictures (scarring of the bile ducts in over 20%)², compared to DBD (6-8%). DCD liver recipients also experience more acute kidney injury than recipients of DBD livers³.

The aetiology of bile duct strictures in donor livers has not been clear but has been thought to be related to clots in the small vessels supplying the bile ducts (the peri-biliary plexus), since the appearance is similar to that seen when the arterial supply to the liver is lost. The peri-biliary thrombi have been assumed to form during the period of hypoperfusion and circulatory arrest, but this is unlikely since they occur in settings where the donor is heparinised before withdrawal of treatment (such as occurs in Belgium).

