5.3 Number of Subjects

Around 60 transplant patients will be recruited. However, since approximately a third of DCD livers undergoing NESLiP will not pass viability criteria, approximately 45 DCD livers will need to be perfused. Similarly, around 15% of DBD livers undergoing perfusion do not pass viability criteria so around 35 DBD livers will need to be perfused.

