5.5 Study duration

The study will continue until all the subjects are recruited. In a normal year, Cambridge perfuse 25 DCD livers and 25 DBD livers and the Royal Free a similar number. Recruitment should thus be complete within a year and possibly sooner, allowing for patients declining consent and livers not being viable.

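### Section 10.6 was not updated for the DBD cohort: it compares a half-DBD pilot with historical DCD recipients only, matched on an agonal phase that DBD donors do not have

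*Protocol*

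**What the plan says.** Section 10.6 fixes three things: the comparator, the ratio and the matching variables. Recipients in the pilot, with no restriction by donor type, are to be "compared with twice the number of recipients of DCD livers that were machine perfused in the recipient centres in the previous 2 years". Of the comparators it adds: "They will be matched for agonal phase duration, cold ischaemia time and UK donor liver index". Donor type is not a matching variable, and no DBD comparator is named.

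Section 10.2 sets the cohort: "60 subjects in total, 30 DBD and 30 DCD". The DBD livers were added by amendment 2 (section 2.7.2) as a separate cohort. Section 4.1 says of the brain-dead donor: "The heart is still beating and there is still a blood supply to the organs up to the point they are cooled".

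Other sections name a different comparator. Section 2.9 compares results with recipients randomised to FFP without TPA, and section 10.3 refers to control perfusions. Section 7 makes one transplanted liver in six such a control. Section 10.4.4 does use historical comparators, for the creatinine ratio.

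**The concern.** Section 10.6 reads as a rule written for a DCD-only pilot. Agonal phase follows withdrawal of treatment in a donor who then loses circulation. By the protocol's own description a DBD donor has no such phase, so the match is undefined for 30 of the 60 recipients.

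The analyst then has two ways to proceed, and both go wrong. Ignoring the agonal-phase match for DBD recipients sets a half-DBD group against a DCD-only group, although section 11.3 expects better DBD results on every outcome it splits by donor type. Enforcing the match leaves the DBD half with no historical comparison. Section 5.4 hopes the pilot will help show whether non-anastomotic strictures are abolished and how to power a formal trial, and that outcome has one of the largest expected differences between donor types.

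**Working it through.** **The plan's own figure first.** Section 5.3 states that "approximately a third of DCD livers undergoing NESLiP will not pass viability criteria" and that "around 15% of DBD livers undergoing perfusion do not pass viability criteria". Livers to perfuse = recipients / (1 − proportion failing):
- DCD: 30 / (2/3) = 45
- DBD: 30 / 0.85 = 35.3

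Both agree with the 45 and 35 in sections 5.3 and 10.2, so the same proportions can be used for the historical pool.

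**Expected difference with no TPA effect, if all 60 enter.** Pilot rate = 0.5 × DCD rate + 0.5 × DBD rate; comparator rate = DCD rate. The rates are those in section 11.3. The last column is the probability that a two-sided Fisher test of 60 against 120 gives p ≤ 0.05 in either direction, by exact enumeration with the 60 drawn as 30 DCD and 30 DBD. The 5% level is an assumption, since section 10.5 names the test but no level. The comparators are drawn unmatched.

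| Outcome | DCD | DBD | Pilot vs comparator | Fisher rejects |
|---|---|---|---|---|
| Non-anastomotic stricture | 20% | 8% | 14% vs 20% | 13.2% |
| Early allograft dysfunction | 40% | 25% | 32.5% vs 40% | 14.2% |
| Acute kidney injury | 50% | 35% | 42.5% vs 50% | 13.2% |
| Anastomotic stricture | 20% | 15% | 17.5% vs 20% | 5.2% |
| Retransplantation | 17% | 11% | 14% vs 17% | 5.8% |
| Primary non function | 4% | 1% | 2.5% vs 4% | 1.7% |

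For non-anastomotic strictures the ratio is 14/20 = 0.70, or 8.4 expected events in 60 against 12 at the DCD rate. Rejection in the pilot's favour has probability 13.2% (13.15% before rounding). With 20% in both groups it would be 1.9%.

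**If agonal-phase matching is enforced.** The 30 DBD recipients have no value to match on and leave the comparison. The donor-mix difference goes with them. What remains is 30 DCD recipients against 2 × 30 = 60 historical DCD recipients.

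**Size of the DCD pool (secondary and conditional).** Section 5.5 says that "Cambridge perfuse 25 DCD livers and 25 DBD livers and the Royal Free a similar number". No volume is stated for the third centre.
- Two centres: 2 × 25 × 2 years = 100 perfused; 100 × 2/3 ≈ 67 transplanted.
- Needed for all 60 at 2:1: 120.
- Needed for the 30 DCD recipients alone: 60, about 90% of the 67.
- If the third centre also perfused 25 a year (assumption): 150 × 2/3 = 100.
- To reach 120, the third centre would need x with (50 + x) × 2 × 2/3 = 120, so x = 40 DCD perfusions a year.

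**Size of a DBD pool.** 2 × 25 × 2 × 0.85 = 85 transplanted at the two centres, against 60 needed for the 30 DBD recipients at 2:1.

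**The case against.** The strongest reply is that section 10.6 means the DCD recipients only. DBD was added as a separate cohort, sections 5.8.3 and 10.2 count the two types separately, and a match on agonal phase already excludes DBD donors. On that reading the donor-mix bias and the need for 120 comparators both vanish. This stands as a limit on the size of the problem. It does not rescue the section, which does not state the restriction and would leave half the pilot without a historical comparator.

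Second, the enumeration uses unmatched comparators, whereas 10.6 also matches on cold ischaemia time and the UK donor liver index. That stands: the documents do not show how much of the imbalance this would remove.

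Third, a reader might infer that section 11.3 shows lower DBD rates for nearly every outcome, and so that the primary result is biased as well. It does not. Only six of its 17 items are split by donor type, and the documents give no donor-type figures for post-reperfusion blood loss or for feasibility as such.

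Fourth, a reader might infer that this comparison decides whether a larger trial goes ahead. Section 10.6 does not say so. Section 10.3, which raises that question, refers to control perfusions, and section 2.9 to the randomised FFP-only recipients. Those controls are few (60/6 = 10), and 10.6 is the section headed as the analysis plan, so the conflict is a further reason to correct it.

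Finally, detail may sit in an analysis plan that is not at hand. That would excuse an omission. Here the protocol itself fixes the comparator and the matching variables, and they do not fit the cohort.

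**Conclusion.** Wrong as written. Section 10.6 specifies a DCD-only comparator and an agonal-phase match for a cohort that is half DBD. Its consequence depends on how it is carried out:

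- If all 60 recipients enter, the six outcomes split in section 11.3 favour the pilot with no TPA effect. Chance rejection is about 13-14% for non-anastomotic strictures, early allograft dysfunction and acute kidney injury, and about 5%, 6% and 2% for anastomotic strictures, retransplantation and primary non function. These figures assume the section 11.3 rates, an equal donor mix, unmatched comparators and a two-sided 5% level.
- If the agonal-phase match is enforced, there is no such bias, but the 30 DBD recipients have no historical comparator.

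It would go too far to say that the historical pool is certainly too small. The shortfall of about 67 against 120 arises only if all 60 are matched, and only if the third centre perfuses fewer than about 40 DCD livers a year. If only the roughly 50 TPA-treated recipients were matched, 100 would be needed, which equals the assumed three-centre pool. For the DCD recipients alone the pool suffices, but with little left over to match on three variables.

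**What to change.** Reword section 10.6 to:
- compare DCD recipients with historical DCD recipients, and DBD recipients with historical DBD recipients;
- use agonal phase duration as a matching variable for DCD only;
- report results by donor type, and stratify any pooled comparison by donor type;
- state the ratio as up to 2:1, as the available pool allows;
- state how the historical comparison relates to the comparison with the FFP-only or control perfusions in sections 2.9 and 10.3, so that the three sections agree.

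The cost is the rewording and the retrieval of past DBD perfusion records at the centres. No extra patients are needed.

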4.3 Investigational treatment

Alteplase (Actilyse, Boehringer Ingelheim, Germany) is a tissue plasminogen activator used routinely for the treatment of thrombotic occlusive events. *In vivo* it relies on the presence of plasminogen in clots and in the circulation which it breaks down to form plasmin, which is the active lytic component. Alteplase has a very short half-life *in vivo* (5 minutes according to the Summary of Product Characteristics, SmPC ⁶).

In the *ex situ* circuit there is no plasminogen circulating, although the liver will make some as time progresses; instead a plasminogen source is required and is readily available in the form of fresh frozen plasma (FFP) which has previously been shown to be effective as a perfusate component in NESLiP ⁷ as well as being a good source of plasminogen ⁸.

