8.1 Liver perfusate

The OrganOx perfusate will be the same as routinely used in the centre, and will comprise 3 units of packed red cells, a plasma substitute (human albumin in Cambridge, Gelofusine at the Royal Free) together with the standard additives and infusions.

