11.6.3.2 Follow-up reports of SUSARs

In case of incomplete information at the time of initial reporting, all the appropriate information for an adequate analysis of causality should be actively sought from the reporter or other available sources. The sponsor should report further relevant information after receipt as follow-up reports.

In certain cases, it may be appropriate to conduct follow-up of the long-term outcome of a particular reaction.

12 Data handling and record keeping

Data will be collated on a password controlled study database held on an encrypted partition of computer hard disc, or trust or university server.

13 Direct access to source data / documents

The investigators will permit trial related monitoring, audits, REC review, regulatory inspections.

14 Publications policy

Authorship will follow the guidelines of the International Committee of Medical Journal Editors (ICJME)¹ based on satisfying the following 4 criteria

- Substantial contributions to the conception or design of the work; or the acquisition, analysis, or interpretation of data for the work;
- Drafting the work or revising it critically for important intellectual content;
- Final approval of the version to be published;
- Agreement to be accountable for all aspects of the work in ensuring that questions related to the accuracy or integrity of any part of the work are appropriately investigated and resolved.

15 Finance

Since the intervention is to be in patients already having a DCD liver which is to undergo *ex situ* perfusion, the only study related expense is the provision of alteplase and fresh frozen plasma. This cost will be borne out of local funds at each participating hospital.

Subsequent analyses on biopsies and perfusate will be funded from future grants.

16 Ethical considerations

The investigators do not envisage any unusual ethical issues.

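### The historical contrast in section 10.6 estimates the TPA+FFP regimen plus any period or centre-mix effect, not TPA, and the section leaves out the randomised FFP-only controls

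*Protocol*

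**What the plan says.** Protocol 10.6 (Analysis plan) takes the transplant recipients in the pilot, without separating those allocated TPA from those allocated FFP alone. They are to be "compared with twice the number of recipients of DCD livers that were machine perfused in the recipient centres in the previous 2 years". On the choice of comparators it says: "They will be matched for agonal phase duration, cold ischaemia time and UK donor liver index". Centre is not listed, and the concurrent controls are not mentioned.

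On the perfusate, 8.1 says "The OrganOx perfusate will be the same as routinely used in the centre" and lists packed red cells with "a plasma substitute (human albumin in Cambridge, Gelofusine at the Royal Free) together with the standard additives and infusions". It gives no colloid for the third centre. FFP enters in 8.2 as about 250 ml per liver. Section 4.3 explains why it is needed: "In the *ex situ* circuit there is no plasminogen circulating". It also describes FFP as a component "which has previously been shown to be effective as a perfusate component in NESLiP".

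On concurrent controls, section 7 randomises one transplanted liver in six to FFP without TPA. Sections 2.9 and 10.3 say that TPA results will be compared with these controls, and 5.6.2 lists D-dimer release against controls as a secondary endpoint.

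**The concern.** Section 10.6 is the section headed as the analysis plan, and it names only the historical comparison. If the historical livers had no FFP, the two cohorts differ in FFP, in calendar period and possibly in centre mix, as well as in TPA. The protocol itself gives a reason to expect FFP to have some effect of its own. Pooling the FFP-only recipients with the treated ones blurs the contrast further.

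This matters because 4.9.2 and 5.4 want the pilot to supply efficacy data for powering a larger trial. The historical comparison is numerically much larger than the randomised one, so it is the one more likely to reach significance and be carried forward. Section 10.4.4 also relies on historical comparators for kidney injury.

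**Working it through.** **1. The protocol's own figure.** With one third of DCD and 15% of DBD livers not viable (5.3), the livers to perfuse are 30/(1 − 1/3) = 45 and 30/(1 − 0.15) = 35.3. Both agree with the 45 and 35 in 10.2. The one-third loss is used again in step 7.

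**2. Did the historical livers receive FFP?** No section says so either way. Three places point to no: 8.1 does not name FFP in the routine perfusate, 4.3 says the circuit has no circulating plasminogen without an added source, and section 15 (Finance) states that "the only study related expense is the provision of alteplase and fresh frozen plasma". This is a strong inference and not a stated fact, because the standard additives in 8.1 are not itemised.

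**3. What each contrast estimates.** On an additive risk scale, let T be the effect of TPA given FFP, F the effect of FFP, and P any period or centre-mix difference. One recipient in six is FFP-only.

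| Contrast | Estimates |
|---|---|
| TPA+FFP against history | T + F + P |
| FFP-only against history | F + P |
| All pilot recipients against history (10.6 as written) | (5/6)T + F + P |
| TPA+FFP against randomised FFP-only | T |

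Pooling therefore dilutes T by one sixth and keeps F and P in full. For example, if F = P = 0 and TPA lowers risk by 20 points, the pooled contrast shows 5/6 × 20 = 16.7 points.

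**4. Size of an FFP effect.** Inputs: DCD non-anastomotic stricture rate 20% (11.3); 30 DCD pilot recipients against 60 historical; Fisher's exact test (10.5). Assumptions: two-sided alpha 0.05 (not stated), T = 0, P = 0, and FFP alone lowers the rate as shown. Exact enumeration gives:

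| Rate under FFP | Apparent benefit | Probability of significance |
|---|---|---|
| 20% | 0 points | 3.6% |
| 15% | 5 points | 6% |
| 10% | 10 points | 16% |
| 5% | 15 points | 40% |

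**5. Size of the randomised contrast.** Controls: 60/6 = 10, of whom 30/6 = 5 are DCD, leaving 50 and 25 on TPA. With 0/25 on TPA, one stricture among 5 controls gives p = 0.167 and two give p = 0.023, so at least two are needed. At 20% risk that has probability 1 − 0.8⁵ − 5 × 0.2 × 0.8⁴ = 1 − 0.328 − 0.410 = 0.26. With both donor types the control rate is (20% + 8%)/2 = 14%, and 10 against 50 with 0% on TPA has power of about 42%. The historical 60 against 30 has about 93% for 20% against 0%, if all 30 pilot recipients have zero risk.

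**6. Centre.** Bias = (difference in risk between centres) × (difference in centre share between cohorts). The documents give neither figure. Assuming risk differences of 5 to 20 points and share differences of 10 to 50 points, the bias runs from 0.05 × 0.10 = 0.5 points to 0.20 × 0.50 = 10 points. If the shares are equal it is zero.

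**7. Can centre be matched?** Section 5.5 gives 25 DCD perfusions a year in Cambridge and a similar number at the Royal Free. Over two years, and counting only livers transplanted, that is 25 × 2 × 2/3 = 33 per centre. If each of these two centres recruits 15 DCD recipients, 2 × 15 = 30 are needed. No volume is given for the third centre.

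**The case against.** The strongest answer is that the protocol already provides a contrast free of FFP confounding. Sections 2.9, 7 and 10.3 plan TPA+FFP against concurrent randomised FFP-only livers. The synopsis, 5.6.1 and 5.7 define the intervention as TPA with FFP, so a historical contrast of the combined regimen fits the stated objective. A reader might infer that the plan credits TPA with the effects of FFP, or that it never uses the FFP-only recipients. The documents support neither: 10.6 makes no claim about TPA alone, and other sections do use those controls. What stands is that 10.6 does not mention them, pools them with treated recipients, and does not say what its own contrast estimates.

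On centre, comparators come from the recipient centres and study livers use each centre's routine base perfusate, so bias is possible and not certain. That is correct, but the three listed variables do not ensure an equal centre mix.

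Matching detail is often left to a statistical analysis plan, and none is shown here. Section 10.6, however, fixes the comparator and the matching list itself, so it can be judged on what it fixes.

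A reader might also think exact centre matching is easy, because 25 × 2 = 50 DCD livers per centre exceeds 30. Those are livers perfused; 10.6 needs transplant recipients, of whom there are about 33.

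**Conclusion.** The point holds in limited form. The historical contrast in 10.6 estimates the TPA+FFP regimen plus any period or centre-mix effect. As written it also dilutes the TPA part by one sixth, assuming the one-in-six allocation is achieved. It cannot isolate TPA, and 10.6 does not direct the reader to the randomised contrast that can.

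The absence of FFP in the historical livers is inferred from 4.3, 8.1 and 15. The 6% to 40% chance of a significant result with an inactive TPA rests on assumed FFP effects of 5 to 15 points and an assumed alpha of 0.05. The centre bias of 0.5 to 10 points rests on assumed differences and vanishes if the centre mix agrees.

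The randomised contrast is unconfounded by FFP but imprecise, with about 26% power for DCD strictures falling from 20% to 0%. That is a reason to report it with its uncertainty. It does not make the historical contrast a substitute for it.

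**What to change.** Revise 10.6 as follows:

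- **State the estimands.** Say that the TPA effect is read from TPA+FFP against the concurrent randomised FFP-only livers, in line with 2.9 and 10.3. Label the historical contrast as the effect of the TPA+FFP regimen, with period effects not excluded.
- **Do not pool.** Compare TPA+FFP recipients with history. Show FFP-only recipients beside their matched historical recipients as a separate descriptive row. For DCD this is about 5 against 10, too few for inference.
- **Handle centre.** Balance on centre within the matching where the pool allows; otherwise stratify or adjust the comparison by centre. Report the centre mix of both cohorts either way.

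The cost is wording and one more descriptive row from data already being collected. The trade-off is in the matching: with about 33 candidates per centre for 30 places, requiring exact centre agreement on top of agonal phase, cold ischaemia time and donor liver index may worsen the match on those three or leave recipients unmatched. Exact centre matching should therefore not be mandatory. The third centre's DCD volume should be obtained before the choice is made.
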